14.6.5 Vital Sign Measurements

Descriptive summary statistics for vital sign parameters and changes from baseline will be tabulated by treatment group. Variables summarized include systolic blood pressure (mmHg), diastolic blood pressure (mmHg), pulse rate (bpm), respiratory rate (per minute), and body temperature.

14.6.6 12-Lead Electrocardiograms

The observed values and change from baseline for each ECG measurement day will be summarized with descriptive statistics. Electrocardiogram variables include heart rate, PR, QT, QTc, RR intervals, and QRS duration. In addition, QT interval with Fridericia correction (QTcF) will be calculated.

An outlier analysis will be performed including all maximum individual postdose measurements (not the mean data), including all repeat and unscheduled readings. All incidences of maximum QTcF (>450 and \leq 480, >480 and \leq 500, and >500 ms), and all incidences of maximum change from baseline in QTc and QTcF (>30 and \leq 60 and >60 ms) will be flagged on the listing. More details on the analyses will be included in the SAP.

14.7 Baseline Characteristics and Other Summaries

Descriptive summaries of demographic and baseline characteristics will be tabulated for both Safety Analysis Set, PK Analysis Set, and FAS. Descriptive statistics or a frequency table, whichever is appropriate, will be provided for age, age group (<65 years or \geq 65 years), height, weight, body mass index (BMI), and BMI distribution (<30 kg/m² or \geq 30 kg/m²). Surgical approach (open versus laparoscopic), surgery duration (hours), time from first dose of study medication to the scheduled start of surgery (hours), type of surgery, primary indication for surgery, and thoracic epidural use will be summarized. Medical history findings will be coded according to MedDRA. Findings will be tabulated by preferred term within system organ class and summarized using number and frequencies.

The number and percentage of subjects who are randomized, treated, complete study treatment, and complete the study will be summarized. The same data will be summarized by site as well. Reasons for discontinuing the study will also be summarized.

Subjects in each analysis population, and those excluded from each analysis population and reasons for exclusion will be summarized using number and frequency. Individual subject listings will also be provided.

14.7.1 Analysis of Adjudicated Hepatobiliary Adverse Events

The independent CEAC adjudicated hepatobiliary AE database will be the primary data source for determining the type and incidence of hepatobiliary AEs. The incidence of the adjudicated hepatobiliary AEs and the difference in these events across treatment groups will be summarized. This analysis will serve as the primary evidence base for determining the risk for DILI in TU-100 and placebo treated subjects.

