6.2.2 Secondary Efficacy Endpoints

The secondary efficacy endpoints are as follows:

- Time to GI-2 recovery (i.e., time to first toleration of solids AND time to first BM)
- Time to ready for discharge (based solely on GI recovery)
- Time to discharge order written
- Length of hospital stay (based on calendar day of discharge order written)
- Proportion of GIR responders
 - GIR by day
- POI-related morbidity (primary POI only)
 - POI that required readmission within 7 days of discharge, or

- Need for postoperative NGT insertion to manage symptoms of POI (i.e., vomiting/retching, abdominal distension) per protocol guidelines
- Time to first toleration of clear liquids, i.e., time at which the subject transitions from clear liquids to the next diet stage (full liquids or solids)
- Time to first BM
- Time to absence of distension and presence of bowel sounds and flatus (i.e., time to when all 3 conditions have been achieved)
- Time to toleration of solids (i.e., able to eat a meal that requires chewing without a vomiting episode by the time the next consecutive meal is offered).
 - Note, if the first solid meal is consumed on the day of hospitalization (i.e., the day of surgery), the time to toleration of solids is as stated (e.g., the time to eat solids without a vomiting episode by the time the next consecutive meal is offered). Further, if the first solid meal is consumed on the day of discharge, the time to toleration of solids criteria is met if there is no vomiting prior to discharge. In all cases, the actual time that should be recorded on the eCRF is the time the meal was consumed by the subject, not the cutoff time for vomiting prior to next consecutive meal or discharge.

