7.2 Discussion of Study Design

The clinical development program is designed to explore the benefit of TU-100 given after BR surgery to prevent the occurrence of POI and as adjunct to ERAS. Previous studies with TU-100 showed that it was generally well tolerated. In completed Phase 2 studies in the US, while primary efficacy endpoints were not achieved, it should be noted that these studies were not designed to evaluate the effect of TU-100 compared with placebo on GI recovery or POI; therefore, the question regarding potential benefit after BR remains unanswered. However, there were signals that TU-100 had an impact on GI recovery after colorectal resection, including less need for nausea medication and a lower number of adverse symptoms.

The in-hospital observation period is up to 10 days after GI surgery. TU-100 is administered in addition to the routine standard of ERAS care (see [Section 10.2.1](#)) and provides a multimodal approach in order to enhance recovery after surgery. Treatment with TU-100 should begin immediately after randomization to provide its effect on GI recovery and ERAS. Hospitalization of subjects provides a controlled setting to assure compliance with study drug administration and allows accurate monitoring of efficacy and safety measures by study staff.

The following provides a rationale for the duration of in-hospital dosing:

- The most favorable benefit-risk profile for TU-100 was expected to occur within the period of highest risk for delayed GI recovery and associated complications, i.e., during the subject's hospital stay.
- Based on TU-100's mechanism of action and the clinical presentation of POI, it is anticipated that the optimal dosing duration is beginning the day after surgery and

continuing through the early postoperative period, during which GI motility should be resuming.

- Discontinuing TU-100 at discharge is appropriate as surgical patients are routinely not discharged before achieving GI recovery milestones. Continuing dosing after discharge would offer no further substantive benefit to the subject and cause unnecessary drug exposure.
- In-hospital dosing allows for close oversight of subjects for both safety and efficacy.

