- ^m Samples for routine clinical liver function tests will include alkaline phosphatase, aspartate transaminase, alanine transaminase, total and direct bilirubin, prothrombin time and INR. If these tests have been performed within 28 days before surgery, but before consent is obtained, the LFTs need not be repeated unless deemed appropriate by the investigator. On Day-1 LFT do not have to be repeated if done within 14 days of Surgery and the LFT were within normal limits. On Day 1, this should be taken before study drug administration to represent baseline values. Liver functions tests to include PT/INR and will be obtained during screening, pre-surgery, Randomization Day 1, Day 4, Day 7, and Day 10 (if remaining in the hospital), and the day of hospital discharge. Liver function tests are needed at the 30-day follow-up visit only if LFTs were elevated at discharge and trending down. If a subject remains in the hospital for an AE of elevated tests, then levels will be followed until resolution. A local laboratory should be used for screening and before pre-surgery Day -1. A central laboratory should be used after randomization on Day 1 and future visits.
- ⁿ Subjects will be randomized 1:1:1 (TU-100 15 g: TU-100 7.5 g: placebo) and stratified by surgical approach (open versus laparoscopic). Study drug will be administered TID (3 times per day [i.e., 6 hours ± 1 hour apart]).

- ^o GI assessments are to be performed twice daily, morning and afternoon with assessments separated by at least 6 hours.
- ^p Subjects will record the following items in their eDiaries on all postoperative in-hospital study days: first flatus (record in real time), first BM (record in real time), nausea occurrence and bothersomeness (24-hour reflection), vomiting/retching occurrence/number of episodes (24-hour reflection), abdominal bloating occurrence and bothersomeness (24-hour reflection).
- ^q Blinded review and assessment of hepatobiliary AEs by an independent CEAC will be performed on an ongoing basis during the conduct of the study.
- ^r PK samples will be drawn only at designated sites at the following times below, and at early termination (not needed at hospital discharge). If a subject is terminating early on a day scheduled for a blood draw, a second sample on the day of termination should be taken if possible. If a subject is terminating early on a day not scheduled for a blood draw, at least 1 sample should be obtained that day if possible.

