10.2.4 Follow-up Period

Follow-up contact (10 to 14 days after last dose of study drug)

All subjects will be contacted via telephone (or in-person if still in the hospital) within 10 to 14 days after the last dose of study medication for follow-up that will include:

- Record concomitant medications
- Monitor AEs
- Review of data for hepatobiliary AEs
- Monitor prespecified postoperative complications
- Determine whether hospital readmission occurred and reason for readmission

A certified letter will be sent to any subject not contacted after 3 attempts by telephone.

Follow-up visit (30 days + 15 days after hospital discharge)

All subjects are to return for a follow-up visit 30 days (+ 15 days). Procedures to be conducted at this visit include:

- Perform physical examination, including weight. Any clinically relevant physical abnormalities (with the exception of surgical scars) that were not present at screening should be recorded as AEs.
- Record vital signs (blood pressure, heart rate, respiratory rate, and temperature)
- Record concomitant medications
- Monitor AEs
- Monitor prespecified postoperative complications
- Determine whether hospital readmission occurred and reason for readmission
- If elevated at discharge and trending down, then liver tests will be completed at the 30-day follow-up visit. If a subject remains in the hospital for an AE of elevated tests, then levels will be followed until resolution.

If a patient does not return for a scheduled visit, all necessary measures should be taken to contact the patient and document the patient's outcome.

Reasonable efforts should be made to contact subjects who are lost to follow-up. A certified letter will be sent to any subject not contacted after 3 attempts by telephone. These efforts must be documented in the subject's file.

Exceptional measure for COVID-19

Depending on the COVID-19 situation (and/or to reduce burden of patient travel as needed), measures below may be considered for the 30-day follow-up visit.

- Window for the 30 day follow-up can be extended to +15 days after hospital discharge.
- If subject is unable to come to clinic for in-person visit, then performing LFT laboratory tests (if needed) at a local hospital, or regional independent laboratory located near the subject will be considered. Local laboratory results should be documented in subject's file.

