14.6.4 Clinical Laboratory Parameters

Clinical safety laboratory tests will be conducted by local or central laboratories. Summary statistics for actual values and for changes from baseline will be tabulated for hematology and chemistry (with a focus on liver transaminases and LFTs) results by treatment group. Clinical laboratory data and vital signs will be summarized using descriptive statistics, including mean values and mean change from baseline values, as well as numbers of subjects with values outside limits of the normal range at each time point. Shift tables for clinical laboratory parameters will be provided to assess the changes in laboratory value from baseline to post-baseline visits. Normal reference laboratory range will be used to determine the number and percentage of subjects who had shifts. Subjects with clinical laboratory values outside of the normal reference will be listed. The number and percentage as well as the listing of subjects who meet the criteria of Hy's law (with ALT or AST values \geq 3 times the ULN [$3 \times$ ULN] and total bilirubin \geq 2 times the ULN [$\geq 2 \times$ ULN]) will be summarized by post-baseline time point and treatment group.

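### Scheduled liver tests able to find a new symptom-free elevation end at discharge, so if TU-100 shortens stay the crude laboratory-detected incidence will be lower in that arm at equal risk

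*Combined protocol and SAP*

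**What the plan says.** **Testing schedule.** Table 1, footnote m (section 10) sets the liver tests from randomization onward at "Randomization Day 1, Day 4, Day 7, and Day 10 (if remaining in the hospital), and the day of hospital discharge". After discharge the same footnote says: "Liver function tests are needed at the 30-day follow-up visit only if LFTs were elevated at discharge and trending down". Section 10.2.4 repeats that condition.

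**Discharge as an outcome.** Section 6.2.2 lists time to ready for discharge, time to discharge order and length of stay as secondary efficacy endpoints. Section 7.2 gives the link to recovery: "surgical patients are routinely not discharged before achieving GI recovery milestones". All dosing is in hospital (section 9.1), so exposure ends at discharge too.

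**Analysis.** Section 14.7.1 says of the adjudicated database: "The incidence of the adjudicated hepatobiliary AEs and the difference in these events across treatment groups will be summarized", and makes this the main evidence on DILI risk. In section 14.6.4, subjects meeting the Hy's law criteria "will be summarized by post-baseline time point and treatment group"; out-of-range values are counted at each time point. Section 14.6.1 summarizes doses and days on drug by arm, but no liver analysis uses exposure or tested time as a denominator.

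**Events outside hospital.** AEs are collected until the follow-up visit (section 12.6.1), and cases meeting the close-observation criteria are reportable up to 30 (+15) days after discharge (section 12.6.8).

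**The concern.** For a subject whose liver tests are normal on the discharge day, no later test is scheduled. A new rise in ALT, AST or bilirubin without symptoms can therefore be found only between first dose and discharge, and the length of that period depends on an outcome the drug is meant to improve. Two arms with the same daily risk would show different crude percentages of laboratory-detected abnormalities if their stays differed.

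The by-time-point display in section 14.6.4 does not cure this. Days 4, 7 and 10 include only subjects still in hospital, who are the slower to recover, and the discharge draw falls on a different day for each subject.

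Comparing hepatobiliary AEs with placebo is a secondary objective (section 6.1.2). If efficacy is good, a modest true excess in laboratory-detected abnormalities could be partly hidden.

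**Working it through.** **The plan's own figures.** The plan gives none for liver events or tested time. The related figure is the design effect in section 14.2, which reproduces. With 122 evaluable subjects per arm (366/3), 244 events, HR 1.428 and one-sided 0.05: √(244 × 0.25) × ln 1.428 − 1.645 = 7.810 × 0.3563 − 1.645 = 1.138, so power is 0.872 against the stated 87%. The planned gain in median GIR is 48 − 34 = 14 h. The documents state no effect on stay; 14 h is used below as an illustration, with 7 h and 0 h beside it.

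**Assumptions not in the documents.** Stay from end of surgery is lognormal with median 84-108 h and log-SD 0.35-0.40. First dose is at 20 h. Abnormalities persist to the next draw, so any onset before discharge is found at the discharge draw. Onset risk is identical in the two arms.

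**Covered time.** Mean covered days = (median × exp(SD²/2) − 20)/24, less 14/24 for the shorter-stay arm. For 96 h and 0.35: 96 × 1.063 = 102.1 h, giving (102.1 − 20)/24 = 3.42 days against 2.84. The detected share is the mean of 1 − exp(−rate × covered days) at constant hazard, and of 1 − exp(−covered days/2) if onset is early (mean 2 days after first dose). Simulation of 400,000 stays gives, for a 14 h shift:

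| Median stay, log-SD | Covered days, placebo | Covered days, TU-100 | Risk ratio, constant hazard | Risk ratio, early onset | Per-day rate ratio, early onset |
|---|---|---|---|---|---|
| 84 h, 0.35 | 2.89 | 2.31 | 0.80 | 0.87 | 1.086 |
| 96 h, 0.35 | 3.42 | 2.84 | 0.83 | 0.90 | 1.085 |
| 108 h, 0.40 | 4.04 | 3.46 | 0.86 | 0.92 | 1.075 |

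Over all combinations tried, the 14 h range is 0.80-0.86 at constant hazard and 0.86-0.92 with early onset. A 7 h shift at constant hazard gives 0.90-0.93, and no shift gives 1.00.

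**Check with a different stay model.** Taking GIR as exponential (medians 48 h and 48/1.428 = 33.6 h), adding an assumed lag of 0-48 h to discharge and an assumed minimum stay of 0-72 h, the covered-time ratio is 0.60-0.81. With the 72 h minimum, closest to the three overnight stays anticipated in section 8.1, it is 0.80-0.81. Early onset in this model gives 0.73-0.95.

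**Size in subjects.** At 10% laboratory-detected incidence on placebo, a 14 h shift shows 8.0-8.6% on TU-100 with no true difference, so a true rate ratio of about 1.17-1.26 would look like none. The gap of 1.4-2.0 points is about 2-3 of 134 subjects. Its standard error is about √(0.10 × 0.90/134 + 0.083 × 0.917/134) = 0.035, so the sampling margin is about ±7 points. At 3% the gap is below one subject.

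**Clinically detected events.** If half of all onsets over an assumed 39 days are found clinically regardless of stay, the ratio at 96 h is (0.5 + 0.5 × 2.84/39)/(0.5 + 0.5 × 3.42/39) = 0.536/0.544 = 0.99. The exponential-GIR model gives 0.98-0.99. The follow-up visit is timed from discharge, so a 14 h (0.58 day) shift changes the whole window of about 33-49 days (covered time plus 30-45 days) by only 1-2%.

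**The case against.** **A reader might infer that no liver test is done after discharge.** That is not so. A 30-day test is planned for subjects elevated at discharge and trending down, and close observation (section 8.5.1) triggers retesting. Neither schedules a draw for a symptom-free subject who was normal at discharge.

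**A reader might infer that the liver comparison favours TU-100 by construction.** The documents do not support this. They state no planned effect on stay; section 5.3 reports only a numerically lower stay in an earlier trial. With equal stays the bias is nil, and with longer stays it reverses.

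**A reader might apply 0.80-0.86 to the whole of section 14.7.1.** That analysis counts adjudicated AEs, which are collected in every arm to the follow-up visit. Which events qualify is left to the committee charter (section 12.6.1), so the laboratory-only share is unknown. Only that share is exposed.

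**A reader might want a per-day rate as the main comparison.** For adjudicated events this would be wrong. Events found weeks after discharge would be divided by in-hospital days; with equal events in both arms, the covered days above give a false ratio of 1.17-1.25 against TU-100 (4.04/3.46 to 2.89/2.31). For laboratory-detected events, early onset still gives a false per-day ratio of about 1.08.

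**Two further points stand.** A shorter stay also means less drug, so part of a lower incidence would be a real effect of the regimen; crude percentages cannot separate this from lost detection. And section 14.1 defers detail to an SAP, which may add such an analysis; no such analysis appears in the documents reviewed.

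**Conclusion.** The point holds in conditional form. Scheduled detection of new symptom-free elevations ends at discharge, discharge may be moved by treatment, and the planned liver tables carry no measure of tested time. If stay is 14 h shorter on TU-100, the apparent risk ratio for laboratory-detected abnormalities at equal risk is 0.80-0.86 under constant hazard and about 0.86-0.92 under early onset. These figures rest on assumed stay lengths, first-dose time and onset patterns; the exponential-GIR model widens them to 0.60-0.81 and 0.73-0.95. They do not carry over to events found clinically, which are largely unaffected. In subjects the effect is small next to sampling error. It bears on how a reassuring liver table is read after a good efficacy result and does not undermine the safety comparison as a whole. It is a cheap improvement.

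**What to change.** 1. **Section 14.6.4.** Keep the crude tables. Add LFT-covered subject-days per arm (first dose to last scheduled LFT). As a supplementary comparison, add the rate of laboratory-detected abnormalities per covered day with its ratio versus placebo. In this rate, stop counting days at a subject's first abnormal draw, so that a stay prolonged by elevated tests does not enlarge its own denominator.
2. **Section 14.7.1.** Keep adjudicated events as incidence over the common window to the follow-up visit, split into those detected by laboratory test in hospital and those detected clinically. Do not divide post-discharge events by in-hospital days.
3. **Consistency.** Table 1 marks the hepatobiliary data review at the 30-day visit, but the list for that visit in section 10.2.4 omits it. Reconcile the two, since the common window depends on it.

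**Cost.** SAP wording and a few table columns. Draw dates, dosing times and the adjudication case data are already collected, and no extra blood draw is needed.

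**Downside.** The rate assumes a roughly constant hazard and can lean against the shorter-stay arm (about 1.08 at 14 h) if onset is early. It should be read beside the crude table, not as the lead result.

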14.8 Pharmacokinetic/Pharmacodynamic Analysis

Plasma concentrations of the HAS and HBS (the major constituents of TU-100) will be summarized for each treatment group. Plasma concentrations of other constituents of TU-100 may also be summarized based on the ability to detect their presence in the collected blood samples. Exploratory population PK/pharmacodynamic analyses may be conducted to understand the exposure response relationships between TU-100 and efficacy and safety data. Data may be used for future population PK analyses which, if conducted, will be reported separately.

14.9 Interim Analysis

No interim analysis is planned.

14.10 Data Independent Committees

There will be 2 independent committees. Each will have a formal charter and their specific roles will be discussed within the protocol.

- DSMB for clinical trial safety oversight
- CEAC for assessment of hepatobiliary AEs

An independent DSMB will be established to conduct safety reviews on periodic safety data cuts and will follow an approved DSMB charter. The DSMB will communicate back to Tsumura about their assessments. Detailed information on the role of the DSMB and frequency of meetings will be provided in the DSMB charter separate from this protocol. The DSMB will be responsible for safety review and oversight of aggregate data from participants. They are not responsible for review of individual participant efficacy data (i.e., GIR determination).

The CEAC blinded to treatment assignment is distinct from the DSMB and will only focus on assessment of hepatobiliary AEs. The CEAC adjudicated hepatobiliary AE database will be used to determine the risk for hepatobiliary AEs. Detailed information on the role of the CEAC and frequency of meetings will be provided in the CEAC charter separate from this protocol.

